Phase (Aim 3; see Fig.2). For phases 1 and 2, we will identify 15 representative clinicians working in FQHCs partnering with the AIMS Center and in the WWAMI region Practice and Research Network (WPRN). For phase 3, we will work with the Wyoming Family Practice Center in Casper, WY, a community health center that provides integrated mental health care to over 25,000 patients yearly (40% are on Medicaid or Medicare; see letter of support) to identify 6 representative clinicians and 30 patient participants, ≥18 years old with a PHQ9 of 10-20. The study will be conducted over a 2.5 year period during Y02 through Y04. Steps 1 and 2 will be conducted in the first 9 months of the study and Step 3 in the last 15 months (See timeline).

Phase 1/Aim 1: Discovery (3 months). The purpose of this phase is to uncover usability problems clinicians experience when implementing BA. Drs. [name] and [name] will be responsible for data collection and synthesis in this phase. As is detailed in the **Methods Core**, discovery data collection involves the identification of end-user needs (PAR process), contextual evaluation (IS process), and user testing (UCD process).

Clinician End Users. We will work with 10 PST-PC clinicians and 5 PST-PC naïve clinicians identified through the AIMS Center and through the WPRN. Previously certified clinicians need not be currently using PST-PC. The inclusion of untrained clinicians and previously certified clinicians who have abandoned PST-PC (or modified it for their use) is important to ensure we have a breadth of perspectives from different end-user types. Including naïve clinicians allows us to evaluate first impressions of PST-PC usability.

Identification of user needs. We will conduct semi-structured interviews with the 10 clinicians who were certified in PST-PC previously, using Zoom.com technology. The interview will interrogate challenges they face in implementing PST-PC that are related to (1) workflow, (2) patients they see, (3) PST-PC processes, and (4) any other challenges they may face. Questions will be tied to the seven common problems with usability (see Background Part 3) and CFIR constructs related to Intervention and Individual Characteristics (see **Methods**

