A final prototype will undergo initial feasibility evaluation in pilot field deployments with each clinician using the prototype with one patient. Once we have completed the redesign of BA so that it (1) meets needs of its clinicians and patients (i.e., is useful), and (2) is easy to use and understand (i.e., is usable), we will move to the *Test* phase of this study.

Phase 3/Aim 3: Test phase (15 months). We will conduct a pilot study comparing the modified version of BA to usual care. Therapists will be randomized to either modified BA, and will use their assigned intervention with 5 patients.

Patient eligibility. Patient participants will be identified through each clinic's electronic health record. Participants must be 18 years old or older, suffering from mild to moderate depression. The site champion will identify potential participants from their electronic health records (EHRs) who score between 10 and 20 on the PHQ-9 and will contact potentially eligible patients to conduct a preliminary screening for eligibility, provide a brief description of the study and obtain informed consent.

Clinician training in modified BA. [name] and [name] will train clinicians in the modified BA. We will follow the protocol developed by the AIMS Center, which includes training in basic brief treatment skills, therapeutic elements of the intervention and therapy process. This is followed by simulated case training.

Clinician data collection. Two types of data will be collected, clinician assessment of intervention usability, and clinician ability to learn the intervention and maintain competency. To measure **intervention usability**, clinicians will complete the ALFA-Q Acceptability Scale, the User Burden Scale and the System Usability Scale, which are core measures for this Center (see **Methods Core** for description of scales). **Learnability** of the interventions will be measured in number of role plays needed to reach competency during training. To measure **sustained competency**, clinicians will collect audio recordings of patient sessions for review by experts. Drs. [name] and [name] will conduct these reviews using each intervention's adherence scale. Sustained competency will be defined by (1) time to first session rated < 4 ("good") and (2) number of sessions rated < 4 ("good") once certified. Clinicians will not be given feedback on session performance.

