Patient data collection. We will use the UWAC data portal, which will be based on the UWAC Data portal⁸⁴ designed specifically for research on mobile depression interventions to confirm eligibility, complete the consent process, and conduct baseline and outcomes assessment (see **Methods Core** for further details.) For qualitative interviews, we will use Zoom.com, a secure teleconferencing service with HIPAA-compliant data security features and the capacity to record sessions. Patients can participate either by phone or video. Participants will receive \$20 for completing each of 2 (baseline and post-treatment) assessments. Patient data will be collected before treatment initiation and after treatment ends. Patients will complete a demographic survey to determine gender, age, race/ethnicity, income categories, and educational level. Patients will complete a series of brief clinical measures to determine the presence of a depressive disorder and if there are any important comorbidities. The *Sheehan Disability Scale (SDS)*^{85,86} is a brief analog scale measuring functioning in work, social, and health domains, using visual-spatial, numeric and verbal anchors. The scale has been validated in medical and psychiatric populations with a variety of psychiatric diagnoses.^{85,86} The *9-item Patient Health Questionnaire*⁸⁷ (PHQ-9) consists of 9 DSM depression symptoms and one disability item. It has been found to have excellent sensitivity to change over time (sensitivity = .88, sensitivity = .80).⁸⁸

Data analysis. Aim 3 focuses on pilot feasibility data to inform a larger (future) clinical trial comparing modified BA to usual care. Thus, analyses do not focus on hypothesis-driven inferential statistics but rather on descriptive statistics, graphical summaries, and basic effect sizes. **H1: Usability.** Differences in clinician-reported usability

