between modified BA and usual care will be plotted using a dotplot and tested using a *t*-test using the SUS and UBS as dependent variables. **H2: Fidelity/Competence:** A similar strategy (dotplot, *t*-test) will be used with number of hours to reach certification. Number of sessions with fidelity scores <4 (“good”) will be summarized as proportions, both by clinician and by treatment. Between-treatment differences will be tested with a 2-sample proportion test. (Future analyses with larger sample size will use a generalized linear mixed model approach to account for the nested data^{89,90}.) **H3: Patient Reported Outcomes.** Histograms and kernel density estimates will be plotted by treatment condition to explore differences on depression outcomes (PHQ-9 total score) and overall daily functioning (SDS). Descriptive statistics (*M* and *SD*) will also be examined by clinician and by treatment, using Cohen’s *d* as an effect size summary. A *t*-test will be used to examine treatment differences in patient outcomes. Of ultimate interest is whether the modified treatment has its impact on patient outcomes through enhanced usability and clinician fidelity. We will use graphical summaries of the data to explore the relationships that are consistent with mediation (e.g., correlation of usability with patient outcomes [b pathway], and treatment differences on patient outcomes with fidelity partialled out [c’ pathway]). The primary focus here is whether the data and relationships appear consistent with mediation, as opposed to a formal test, which will be dramatically under-powered.

Power and Sample Size. Sample sizes for Aims 1 and 2 were based on estimates from the UCD literature on necessary number of participants to capture critical design information, where the recommendation is 5-10 end users. As Aim 3 is focused on gathering information (feasibility, recruitment and retention rates, response and attrition rates, etc.) for a future R01 application, the sample size was set primarily for practical reasons and used estimated effect sizes, rather than being driven by hypothesis testing.

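### The planned patient t-test ignores nesting within provider or team, so its standard error is wrong; the p-value is too small on average if each provider or team serves one arm only

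*Combined protocol and SAP*

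**What the plan says.** All the analysis text is in the Data analysis section of the research narrative that follows the IRB form.

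- **Patient outcomes (H3).** A t-test "will be used to examine treatment differences in patient outcomes". Means and SDs "will also be examined by clinician and by treatment", with Cohen's d as the effect-size summary.
- **Session fidelity (H2).** Sessions rated below 4 are summarised as proportions by clinician and by treatment. Then: "Between-treatment differences will be tested with a 2-sample proportion test".
- **Nesting.** It is acknowledged but deferred: "Future analyses with larger sample size will use a generalized linear mixed model approach to account for the nested data".
- **Role of inference.** The section opens by saying that "analyses do not focus on hypothesis-driven inferential statistics but rather on descriptive statistics".

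The unit through which treatment reaches patients is described in several ways:

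- Phase 3/Aim 3: Test phase (narrative): therapists are randomized and "will use their assigned intervention with 5 patients". The Study Overview plans "to identify 6 representative clinicians and 30 patient participants".
- Section 1.5, Aim 3: a non-randomized comparison. All provider teams in the clinic use the modified treatment (modBA), 10 patients per team and 40 in total, against 40 usual-care patients. The Specific Aims repeat the all-teams assignment.
- Section 5.1, Phase 3 Testing: 11 clinicians and 80 patients. Usual-care patients are those whose providers give usual care.
- Section 5.1, Clinician Procedures: a target of 10 patients per clinic.
- Section 5.1, Patient Procedures: usual-care patients are defined by their own status, as clinic patients whose care does not yet use the modified model.

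**The concern.** Patients treated by the same therapist or team tend to have more similar outcomes than patients of different ones. An ordinary two-sample t-test does not allow for this. When a provider or team belongs wholly to one arm, differences between providers become part of the difference between arms, but the test's standard error barely reflects them. A chance difference between a few providers can then look like a treatment effect. The pooled proportion test on sessions has the same weakness, if it is run.

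No confirmatory decision rests on these tests. What is at stake is how certain the pilot's effect appears when the future trial is planned.

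The by-clinician summaries make provider variation visible, but they are descriptive and do not change the t-test's p-value.

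**Working it through.** **Inputs.** From the documents: 10 patients per team and 40 modBA patients (section 1.5), which implies 40 / 10 = 4 teams; 40 usual-care patients (section 1.5); 6 clinicians with 5 patients each, 6 x 5 = 30 (Study Overview and Phase 3/Aim 3). Not given, and therefore assumed: two-sided 0.05, ICC of 0.02/0.05/0.10, four usual-care teams of 10, and a 3 v 3 split of the six clinicians. The plan states no power, ICC or standard error, so there is no figure of its own to reproduce.

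**Case A: each unit in one arm only.** With m patients per unit, the variance of the arm difference is multiplied by DEFF = 1 + (m - 1) x ICC. The true false-positive rate of the ordinary test is about 2 x [1 - Phi(1.96 / sqrt(DEFF))].

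| Layout | ICC | DEFF | 1.96/sqrt(DEFF) | Formula | Simulated |
|---|---|---|---|---|---|
| 4 v 4 teams of 10 | 0.02 | 1 + 9 x 0.02 = 1.18 | 1.80 | 7.1% | 7.1% |
| | 0.05 | 1.45 | 1.63 | 10.4% | 10.4% |
| | 0.10 | 1.90 | 1.42 | 15.5% | 15.8% |
| 3 v 3 clinicians of 5 | 0.02 | 1 + 4 x 0.02 = 1.08 | 1.89 | 5.9% | 5.8% |
| | 0.05 | 1.20 | 1.79 | 7.4% | 7.5% |
| | 0.10 | 1.40 | 1.66 | 9.8% | 9.8% |

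The simulations used a normal outcome, no treatment effect and 40,000 trials per case. A t-test on one mean per unit rejected in about 5% of trials in every row.

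**Case B: the same four teams supply 10 patients to each arm.** The team effect cancels in the arm difference but still enters the within-arm variance, so the ordinary test overstates the standard error. Simulated false-positive rates are about 4.9%/4.5%/4.2%. A paired test on team means gives about 5%.

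**Power under the unit-level analysis.** The standard error of d is sqrt(2 x DEFF / 40) for 4 v 4 teams of 10, that is 0.24/0.27/0.31, with 2 x 4 - 2 = 6 degrees of freedom. From the noncentral t at 80% power, the detectable d is 0.82/0.91/1.04. If 40 v 40 patients were independent, it would be 0.63.

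**The case against.** The strongest reply is that the direction of the error is not established. A reader might infer that the p-values are certainly too small. The documents do not support that. Section 1.5 and the Specific Aims assign all teams to the modification, and the Patient Procedures define controls by patient status, so the same teams may supply both arms. Then the test errs slightly the other way. This stands, and the conclusion is conditional for that reason. On either reading, though, the test ignores the nesting that the plan itself names.

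A second reply is that the pilot is descriptive, discloses the nesting and shows results by clinician. This also stands and lowers the importance. It does not remove the point, because the tests are still scheduled. Cohen's d as a descriptive summary is unaffected. The plan promises no confidence interval around it, so it cannot be faulted for one that is too narrow.

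Third, the 4 v 4 figure joins the 80-patient layout of the IRB form to a t-test written in the narrative, which plans 30 patients. This is fair. For the 30-patient version, the smaller figures apply.

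Two further readings go too far:

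- **The clinic as the unit of allocation.** Section 5.1 and section 8.2 say only that some clinics had already adopted the model, and section 1.5 speaks of a single clinic. Any clinic-level layout is an assumption.
- **Large error rates for the session test.** These need assumed session counts and event rates. The test may also not be runnable. The narrative says "clinicians will collect audio recordings of patient sessions for review by experts", whereas sections 5.1 and 5.14 describe a clinician self-report checklist.

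**Conclusion.** The point holds in conditional form. The patient t-test uses a standard error that does not fit data the plan calls nested. If each provider or team is in one arm only, as the narrative's Phase 3 text and the usual-care wording in section 5.1 suggest, and the ICC is positive, the p-value is too small on average. It need not be too small in every dataset.

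The direction in that case holds for any positive ICC. The size rests on the assumed ICC, significance level and arm splits: about 7%/10%/16% for the larger layout and 6%/7%/10% for the smaller, against a nominal 5%. If the same teams serve both arms, the error is small and conservative.

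The same flaw applies to the pooled session test, if it is run. Importance is low to moderate.

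**What to change.** 1. Reconcile section 1.5 (Aim 3), section 5.1 (Phase 3 Testing, Clinician Procedures, Patient Procedures), the Study Overview and Phase 3/Aim 3 on the unit, its size and the patient total. State whether any unit contributes patients to both arms.
2. Replace the patient t-test with a comparison of one value per highest-level unit confined to one arm, paired by unit if units are in both arms. Alternatively, fit a random effect for that unit with small-sample degrees of freedom. Clinician means are not enough if the team or clinic is the unit.
3. If only 2 or 3 units per arm remain, drop the p-value and report Cohen's d as exploratory. Any interval given should allow for clustering. For 40 v 40 with d near 0, the 95% half-width is 0.45 if clustering is ignored and 0.59/0.66/0.75 with 4 v 4 teams.
4. Treat any session comparison that can still be run in the same way, in place of the pooled proportion test.
5. Confirm that the de-identified extract carries coded clinician, team and clinic identifiers. The by-clinician summaries already imply a clinician code, but the variable lists in sections 5.2 and 5.7 name none of the three.

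The cost is analysis wording, the reconciliation and possibly extra coded fields. Power is lower, as the detectable d above shows. The change does not remove confounding from non-random allocation.

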Aim 1: Discover Phase (3 months). Using iterative and participatory methods, we will interview up to 15 clinicians from FHQCs affiliated with the WWAMI region Practice Research Network (WPRN, a collaborative group of primary care practices through the states of Washington, Wyoming, Alaska, Montana and Idaho to facilitate innovative community-based research), and observe them in routine practice to identify usability challenges. Contribution to the Center: Data from this phase will be used to inform the Typology of EBPI Targets.

Aim 2: Design/Build Phase (6 months) After identification of potential targets, the research team will work via Zoom teleconferencing with the original clinicians from the discover phase and 0-5 new clinicians to engage in a rapid cycle of iterative prototype development and testing (e.g., storyboarding, paper prototypes) of BA modifications. The build of these modifications will include the development of intervention prototypes for user testing and refinement with input from these care managers. Contribution to the Center: Data from this phase will be used to inform the Matrix of EBPI Modifications.

Aim 3: Test Phase (15 months). We will test and compare the BA modification (modBA) to usual care in a small non-randomized trial. We will assign all provider teams (therapist & care manager(s)) in the clinic to use modBA with 10 patients per team for a total of 40 patients. We will then compare patient outcomes for those receiving modBA vs. 40 patients receiving usual clinic care. **H1:** Modifications developed in the Design/Build phase for targets identified in the Discover Phase will result in better usability (System Usability and User Burden Scales) compared to usual care.

H2: modBA will be more effective than usual care on improving clinical outcomes of functional disability (Sheehan Disability Scale [SDS]), change in depression symptoms over time (PHQ-9 total score), and change in anxiety symptoms over time (GAD-7 total score).

1.6 Study design. Provide a one-sentence description of the general study design and/or type of methodology.

Your answer will help HSD in assigning applications to reviewers and in managing workload. Examples: a longitudinal observational study; a double-blind, placebo-controlled randomized study; ethnographic interviews; web scraping from a convenience sample of blogs; medical record review; coordinating center for a multi-site study.

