Participants must be 18 years old or older, suffering from mild to moderate depression. The site champion will identify potential participants from their electronic health records (EHRs) who score between 10 and 20 on the PHQ-9. Patient procedures include:

- Up to 40 patients who are already receiving care at BVHC will receive care via the BA task-sharing model
- We will also include a sample of up to 40 other patients who are already receiving care at BVHC (but not yet receiving care via the modified BA model) who will continue to receive their usual care
- Patients will complete weekly PHQ and GAD (already being collected by BVHC as part of usual care). This includes both the patients who are receiving care via the BA task-sharing model and those who are receiving care without the model
- We will collect historic patient data (PHQ and GAD, already collected by BVHC and agreed to by patients) for all patient participants. This includes both the patients who are receiving care via the BA task-sharing model and those who are receiving care without the model.
- We will collect 3-month follow up patient data (PHQ and GAD, already collected by BVHC and agreed to by patients) for all patient participants. This includes both the patients who are receiving care via the BA task-sharing model and those who are receiving care without the model.
- We will ask up to 10 patients who received care via the BA task-sharing model to complete exit interviews to give their perspective on the care they received. Patients will be consented for these

interviews, as we will then be asking patients to complete research activities that are beyond activities already completed during their usual care. Patients will be paid \$25 for the exit interviews.

- 5.2 Data variables.** Describe the specific data you will obtain (including a description of the most sensitive items). If you would prefer, you may upload a list of the data variables to the **Supporting Documents** SmartForm instead of describing the variables below.

Clinician Data:

Phase 1 & 2 qualitative clinician interviews:

We request flexibility in qualitative interviewing questions with clinicians during Phase 1 and 2 which will include:

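### Historic, weekly and 3-month PHQ-9 and GAD-7 scores are extracted for every patient, but the patient-outcome analysis is still a t-test from a two-assessment design, with no rule for the repeated scores and no GAD-7 analysis

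*Combined protocol and SAP*

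**What the plan says.** Section 5.1 (Patient Procedures) sets out three streams of scores from the health record:

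- Weekly: "Patients will complete weekly PHQ and GAD (already being collected by BVHC as part of usual care". The text applies this to both groups.
- Historic: "We will collect historic patient data (PHQ and GAD, already collected by BVHC and agreed to by patients) for all patient participants".
- Follow-up: "We will collect 3-month follow up patient data (PHQ and GAD", again for all patient participants.

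The numbers are "Up to 40 patients who are already receiving care at BVHC will receive care via the BA task-sharing model" and up to 40 others who continue usual care.

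H2 in section 1.5 concerns "change in depression symptoms over time (PHQ-9 total score), and change in anxiety symptoms over time (GAD-7 total score", alongside functional disability. The Specific Aims repeat it.

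The analysis text is in the research plan that follows section 13. Its Patient data collection paragraph states: "Patient data will be collected before treatment initiation and after treatment ends". Under Data analysis, H3 plots "differences on depression outcomes (PHQ-9 total score) and overall daily functioning (SDS" and adds means, SDs and Cohen's d. A t-test "will be used to examine treatment differences in patient outcomes". H3 names no time point, change score, summary measure, baseline adjustment or longitudinal model, and it does not mention GAD-7.

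**The concern.** The data section and the analysis section describe different studies. One delivers a series of scores per patient, before and after the start of the modified model. The other expects a single before-and-after pair. H3 also analyses the Sheehan Disability Scale, which is not among the patient variables listed in section 5.2, and omits GAD-7, which is. The analysis text was evidently not updated when data collection moved to the health record.

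Two things are at stake. First, the Data analysis section makes basic effect sizes a main product of the pilot, to inform a later trial. With at most 40 patients per group that estimate is imprecise, and the repeated scores would narrow it without further data collection. Second, the groups are not randomised. The historic scores are the only PHQ and GAD evidence on whether the groups were already moving differently before the start, and no use is planned for them.

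**Working it through.** The documents state no power, SD, effect size or interval width, so there is no figure to reproduce.

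**Inputs from the documents.** Up to 40 patients per group (section 5.1). Ten patients per team and 40 in total (section 1.5, Aim 3), so 40/10 = 4 teams in the modified arm.

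**Assumptions.** Correlation ρ between two scores of one patient; p pre-start and r on-study scores. The only session count in the documents is 6 to 10, for problem-solving treatment rather than BA. I use r = 4 to 10.

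**Variance factors.** A t-test on one post score is set to 1. For constant ρ:

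- t-test on one change score: 2(1−ρ)
- ANCOVA of the mean of r post scores on the mean of p pre scores: [1+(r−1)ρ]/r − pρ²/[1+(p−1)ρ]
- One fixed week, adjusted for p pre scores: 1 − pρ²/[1+(p−1)ρ]

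**On-study average, one baseline.** At ρ = 0.5, r = 8: (1+3.5)/8 − 0.25 = 0.3125, a reduction of 69%. Over ρ = 0.3 to 0.7 and r = 4 to 10, the reduction is 61–76% against one post score and 53–80% against one change score.

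**Final week, one baseline, complete data.** The factor is 1−ρ². For ρ = 0.3 to 0.7 the reduction is 9–49% against one post score and 15–35% against one change score. All of this comes from baseline adjustment; the other post weeks add nothing.

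**Estimand and correlation structure.** Take three pre and four post scores, with 8 weeks between the last pre and first post score. Constant ρ = 0.6 is compared with a correlation that decays as 0.40 + 0.45 × 0.9^lag.

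| Analysis | Constant 0.6 | Decaying |
|---|---|---|
| One pre, one post (first post week), ANCOVA | 0.64 | 0.65 |
| Mean of four post on mean of three pre, ANCOVA | 0.21 | 0.48 |
| Last post week, three pre scores | 0.51 | 0.67 |
| Last post week, one pre score | 0.64 | 0.71 |
| t-test on mean post minus mean pre | 0.23 | 0.59 |

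For example, with constant correlation the second row is 2.8/4 − 1.08/2.2 = 0.209, and the last row is 0.4 × (1/3 + 1/4) = 0.233.

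With three pre and eight weekly scores, arms constrained equal before the start and the effect read at week 8, the factor is 0.28 (constant) or 0.55 (decaying) if the arm effect is a straight line. With free weekly means it is 0.51 or 0.61.

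**Teams.** Repeated scores do not reduce between-team variance. With 10 per team, 9 × ICC is added to both factors being compared. For r = 8, one baseline and ρ = 0.5 to 0.7, the reduction in the on-study average falls to 34–52% at ICC 0.05 and 24–40% at ICC 0.10. At ρ = 0.5, ICC 0.05: 1 − (0.3125+0.45)/(1+0.45) = 47%.

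**The case against.** A reader might infer that the planned t-test throws away at least half of the available precision, or that the interval for d at 40 per group would shrink from ±0.44 (1.96 × √(2/40)) to somewhere between ±0.20 and ±0.30. The documents do not support either. Those figures need an on-study average as the estimand, an unadjusted single-score t-test as the comparator, and correlations and score counts that appear nowhere in the plan. Against single-baseline ANCOVA, the decaying-correlation case moves only from 0.648 to 0.482, a reduction of 26%. For the last post week the factors of 0.51 and 0.67 correspond to about ±0.31 and ±0.36.

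It is also tempting to say that a t-test must discard the series, or that a patient missing one chosen score is dropped. H3 does not say which value enters, and no missing-score rule is given. A t-test on mean post minus mean pre takes one number per patient and uses every score. At constant correlation 0.6 it costs little: 0.23 against 0.21. Since H2 speaks of change over time, that reading is possible. The fault is an unspecified summary, not the t-test itself.

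Finally, this is a descriptive pilot with a sample size set for practical reasons, and confounding is the larger threat. That limits how much weight precision deserves. It does not excuse leaving the summary open, since it could then be chosen after the data are seen. The plan's deferral of mixed models to larger samples sits under fidelity and concerns nesting; it does not address repeated patient scores.

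**Conclusion.** The point holds as a gap between the data collected and the analysis planned. Section 5.1 supplies repeated PHQ-9 and GAD-7 scores and H2 is about change over time, while H3 keeps a two-assessment analysis, gives the historic and weekly scores no role and omits GAD-7. For GAD-7 the fault is omission.

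The cost in precision is real but cannot be fixed at one number. It is roughly 10% to 80% of variance: the low end is a final-week estimand with weak correlation, and the high end is an on-study average over ten scores against a single change score. Between-team variation lowers it. All of these figures rest on assumed correlations, counts and spacing. This is an inexpensive improvement that should be made. It does not invalidate the pilot, and it does nothing about confounding.

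**What to change.** Rewrite H3 for the data in section 5.1, for PHQ-9 and likewise GAD-7:

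1. Name one estimand in advance: the arm difference at a fixed week, or the on-study average. Define each patient's start point, including for usual-care patients, who simply continue their care.
2. Replace the t-test with a linear mixed model on all available scores: time from the start point, arm-by-time, pre-start scores included as baseline, patient random effects and a term for provider team. If the estimand is a fixed week, state whether time is a straight line or free weekly means, because the precision depends on it. A simpler alternative is ANCOVA of the mean on-study score on the mean pre-start score.
3. Report the arm difference with its 95% CI, the standardised effect size, the pre-period trend by arm, and the number of scores per patient by arm.
4. Keep the comparison descriptive and say that the groups were not randomised.

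The cost is analysis-plan wording and modest programming, with no new data. There are two drawbacks. The mixed model assumes that the timing of scores is explained by the observed scores, which is why score counts should be tabulated. With about four teams in the modified arm, the team component will be poorly estimated and its interval should be read with that in mind.
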